8.3 Statistical methods

To assess our intervention, we will fit linear mixed models (LMMs) with single-degree-of-freedom linear contrasts [80] to determine if the data support our predictions (see next section). We will use a linear mixed model with main effects for group (experimental, control) and time (Test) and the group by time interaction simply provides a more flexible approach to the typical analysis of variance (ANOVA) model for a randomized pretest-posttest design. Specifically, LMMs will permit us to account for participant matching with a random cluster effect; and they permit each participant to have her or his initial value (random intercept) and different change patterns across the tests (random coefficients for an underlying piecewise regression). LMMs allow us to use covariates to adjust for any potential confounders. Finally, these models can tolerate missing data on the response, which is not true of the standard ANOVA-based model.

Lesion Reconstruction Methods: [name]'s laboratory personnel will reconstruct stroke lesions from the research grade MRI scans. They will superimpose lesions on each axial slice to identify common areas of lesion overlap associated with damage to the right or left hemisphere and to assess comparability of intrahemispheric lesion location in our two tracks. This grant will not specifically examine intrahemispheric lesion location, but these data will provide pilot data for future studies. To calculate the CST lesion load, we will use the tractography based atlas of human brain connections from the natbrain lab [72]. We will use the MRICron descriptive tool for the calculation of the CST-lesion overlap volume. The binary lesion mask file will be overlaid onto either the left or right binary template CST atlas, and the percentage of CST which overlaps with the lesion is calculated.

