7.2 Study Procedures

7.2.1 Visit 1 (pre-test 1):

Visit 1 (pre-test/screening): subjects will be consented, and then tested using standardized tests including the primary and secondary measures. In addition, the Edinburgh handedness inventory, Confidence in Arm and Hand Movement (CAHM), Multidimensional Scale of Perceived Social Support, NIH stroke scale, tests for comorbidities including testing of grip strength, visual neglect, and apraxia. If they meet criteria for the study, they will be randomly assigned to either the intervention or comparison condition. Tests may be videotaped for scoring and standardization purposes. Participant's names will not be associated with the videotapes. A data safety monitoring board will monitor the study for safety and to minimize risk.

7.2.2 Visit 2 (pre-test 2):

Visit 2 will include the same assessments as visit 1 to establish stability in baseline measures. Participants will also receive an MRI of the brain, which will take about one hour, as long as they are able to have one. The research grade MRI is used for data analysis regarding lesion location and volume. It is standard for studies of this nature to collect this information.

7.2.3 Visit 3-17:

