7.3 Duration of Participation

This study will require each participant to attend three 60-minute sessions per week for 5 weeks, as well as 5 separate test (pre and post) sessions, for a total of 20 sessions. If participant misses a session, it will be made up the following week, or by adding it to the end of training sessions. The first two separate pretests take place at visit 1 and 2, one to two weeks apart. The other additional testing sessions take place the visit after the conclusion of therapy sessions, 2 weeks later, and a 6 months following conclusion of therapy sessions.

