8.2 Sample size determination

Based on our primary outcome measures (Barthel, FIM-motor, Abilhand, UEFM, JTHFT) the proposed sample size of 60 participants per group provides adequate power (≥ 0.80) to assess each prediction when the effect size (Cohen's f) is 0.35 or greater. Cohen suggested that researchers consider $f=0.1$ as a small effect, $f=0.25$ as a medium effect, and $f=0.4$ as a large effect. To determine sample size, we used a power analysis program, SOLO [81], and computer simulation. SOLO permitted us to vary effect sizes and determine the test's power for a fixed group size. The simulation permitted us to use our pilot data to generate multivariate normal data; fit a model with fixed effects for group, test, and group by test interaction; conduct tests to include those for the linear contrasts; and record the p-value and associated effect size. The pilot data was particularly useful because the participants had been chosen so that they would span the expected impairment levels, and included right- and left-hemisphere-damaged participants. We will go through the major measures and analyses for each aim below. We have collected pilot data for 15 participants, using a cross-over design, for Aims 1 and 2, which provide preliminary support for our predictions.

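### The mixed model in Section 8.3 leaves the arms' pre-test means free and names no baseline covariate, so on the natural reading it gives up a small, free gain in precision

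*Combined protocol and SAP*

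**What the plan says.** Section 8.3 specifies a linear mixed model with "main effects for group (experimental, control) and time (Test) and the group by time interaction", a random intercept, and random coefficients for a piecewise change over the tests. The power simulation in Section 8.2 used the same structure: "fit a model with fixed effects for group, test, and group by test interaction".

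The hypotheses are to be tested with "single-degree-of-freedom linear contrasts [80] to determine if the data support our predictions (see next section". The document contains no such section: Section 8.3 ends with lesion reconstruction and is followed by confidentiality. The contrast weights over the five tests are therefore not available.

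On covariates, Section 8.3 says only that "LMMs allow us to use covariates to adjust for any potential confounders". It names none, and the baseline value of the outcome is not mentioned.

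Every participant has two pre-tests. Section 7.3 states "The first two separate pretests take place at visit 1 and 2, one to two weeks apart", and Section 7.2.2 gives the purpose: "Visit 2 will include the same assessments as visit 1 to establish stability in baseline measures". Three post-tests follow (Visits 18, 19 and 20). Random assignment is described under Visit 1 in Section 7.2.1, ahead of the text for Visit 2.

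**The concern.** In a randomised trial the two arms have the same expected mean before treatment. A model with a free group effect at the pre-tests estimates that difference anyway, and the interaction contrast then subtracts the estimate from the post-test difference. The random intercept does not change this: it describes variation between people and does not equate the arm means.

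Subtracting the whole pre-test difference amounts to fixing the slope of post on pre at 1. Under compound symmetry the slope on the mean of two pre-tests is 2ρ/(1+ρ), which is 0.67, 0.82 and 0.89 at ρ = 0.5, 0.7 and 0.8. The excess subtraction adds noise. At stake is a somewhat larger standard error on each primary contrast than the same data could give.

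**Working it through.** **Inputs from the document.** 60 per group, power of at least 0.80 and Cohen's f = 0.35 (Section 8.2); two pre-tests and three post-tests (Sections 7.2 and 7.3).

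**Inputs assumed.** Neither alpha nor the correlation between tests is stated. I take two-sided 0.05, compound symmetry with unit SD and correlation ρ of 0.5, 0.7 or 0.8, independent participants, complete data, and a contrast of one post-test against the mean of both pre-tests.

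**1. The plan's own power statement.** For two groups d = 2f = 0.70. Power ≈ Φ(0.70 × √(60/2) − 1.96) = Φ(3.834 − 1.960) = Φ(1.874) = 0.970 (0.967 with the t distribution). The claim of at least 0.80 is met. The exact basis of the simulation cannot be rebuilt, because alpha and the pilot covariance are not given.

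**2. What the planned contrast estimates.** A mixed model with a free mean for each group at each test was fitted to one simulated five-test data set. The interaction contrast, post minus the mean of the two pre-tests, was 0.441612. The plain difference in mean change scores was also 0.441612.

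**3. Variance per participant.**

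- Change from the pre-test mean: 1 + (1+ρ)/2 − 2ρ = 1.5(1−ρ).
- Adjusted for the pre-test mean: 1 − ρ²/[(1+ρ)/2] = (1−ρ)(1+2ρ)/(1+ρ).
- Ratio, adjusted to change: (1+2ρ)/[1.5(1+ρ)].

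| ρ (assumed) | Change | Adjusted | Ratio | Variance saved | Share of 120 participants |
|---|---|---|---|---|---|
| 0.5 | 0.750 | 0.667 | 0.889 | 11% | 13 |
| 0.7 | 0.450 | 0.424 | 0.941 | 6% | 7 |
| 0.8 | 0.300 | 0.289 | 0.963 | 4% | 4 |

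The last column is 120 × (1 − ratio).

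**4. Simulation check.** Over 6,000 simulated trials of 60 per arm, the variance ratio with a fitted regression was 0.89 at ρ = 0.5 and 0.95 at ρ = 0.7. Estimating the slope costs a little, about 1/(120 − 4) = 0.9% of variance, so the ratios in the table are slightly favourable to adjustment.

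**5. Effect on power.** If d = 0.70 is read in SD units of the change score, power at 60 per group goes from 0.970 to 0.982, 0.977 and 0.974 at ρ = 0.5, 0.7 and 0.8. For an effect at which the planned contrast had exactly 80% power, adjustment would give 84.4%, 82.3% and 81.5%.

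**The case against.** **The contrast is not shown.** The missing text might define weights or covariates that already adjust for baseline. This stands as a limit on certainty: the change-score reading is the natural one for a group by time model, not a stated plan. The covariate sentence leaves room for baseline adjustment without committing to it.

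**The gain is small.** This also stands. The table shows 4% to 11% under assumed correlations. Section 8.3 also allows for matched participants through a random cluster effect. If matching tracks baseline scores, the gain shrinks further. The random piecewise coefficients would also take the covariance away from compound symmetry.

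**Assignment precedes Visit 2.** Since Section 7.2.1 describes assignment at Visit 1, Visit 2 may not be a clean baseline. However, a change from the mean of both pre-tests already takes Visit 2 as unaffected by allocation, so adjusting for that mean assumes nothing more. A reader might infer that only Visit 1 should be constrained, with the effect read as the group term at a post-test. That gives variance 1 − ρ², a ratio to the planned contrast of (1+ρ)/1.5 = 1.00, 1.13 and 1.20 at ρ = 0.5, 0.7 and 0.8: no gain, or a loss.

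**Stronger readings that the documents do not support.**

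- A reader might infer that the pre-tests are thrown away. They are not: test is a factor in the model, and a contrast against their mean uses both.
- A reader might infer a much larger loss by supposing that a single pre-test is the reference. Sections 7.2 and 7.3 describe two and nowhere single one out.
- A reader might infer bias or inadequate power. The contrast is unbiased under randomisation, and power at the planned effect is high.

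**Conclusion.** The point holds as one of efficiency and specification, not validity. As written, Section 8.3 leaves the pre-test means free and commits to no baseline adjustment. For any correlation below 1 under compound symmetry, adjusting for the same two pre-tests is at least slightly more precise, before the small cost of estimating the slope. The size rests on correlations that the document does not give, on compound symmetry and independent participants, and on the assumed contrast. It does not put the trial's stated power in doubt. It is worth acting on because the data are already collected and no stronger assumption is needed.

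**What to change.** In Section 8.3:

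1. State the contrast weights over the five tests for each prediction.
2. For each primary endpoint, pre-specify one of two forms, which are equivalent under the assumptions above:
   - model Visits 18, 19 and 20 with the mean of the two pre-tests as a covariate; or
   - model all five tests with both pre-test means equal across arms, and group by time terms only at Visits 18, 19 and 20.
3. State that Visit 2 is treated as a pre-treatment measure, and that this assumes allocation does not affect it, given that Section 7.2.1 describes assignment at Visit 1.

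This changes SAP wording only. It needs no new visits, data or participants, and no change to the timing of randomisation. It should be settled before outcome data by arm are examined.

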9.0 Confidentiality, Privacy and Data Management

9.1 Confidentiality

9.1.1 Identifiers associated with data and/or specimens

9.1.1.1 Use of Codes, Master List

Each site will have a code linked to subject's identifiable information in a locked document. The list will not be shared between sites or with members that are not part of the research group.

9.1.2 Storage of Data and/or Specimens

Data will be kept electronically on password-protected computers and backed up on external hard-drives locked in filing cabinets in room C2852 at the COM or [name]'s Laboratory at USC. Hardcopies of the data will be kept as well, also locked in room C2852 at the COM or locked in [name]'s laboratory at USC.

9.1.3 Access to Data and/or Specimens

Electronic key card access is required to enter room C2852. A list of approved personnel is kept by the neurology dept. USC also has locks on the door and a list of approved personnel.

9.1.4 Transferring Data and/or Specimens

De-identified data will be collected at both sites (PSU, USC) and managed using REDCap (Research Electronic Data Capture) at Penn State. REDCap is a secure web application designed to support data capture for research studies, providing user-friendly web-based case report forms, real-time data entry validation (e.g. for data types and range checks), audit trails and a de-identified data export mechanism to common statistical packages (SPSS, SAS, Stata, R/S-Plus). The system was developed by a multi-institutional consortium which includes The Pennsylvania State University and was initiated at Vanderbilt University. The database is hosted at the Penn State Hershey Medical Center and College of Medicine data center, which will be used as a central location for data processing and management. REDCap data collection projects rely on a thorough study-specific data dictionary defined in an iterative self-documenting process by all members of the research team. This iterative development and testing process results in a well-planned data

collection strategy for individual studies. REDCap is flexible enough to be used for a variety of types of research and provides an intuitive user interface for database design and data entry. Deidentified data can be sent via password protected files. Videotapes will be shared for standardization and scoring purposes. They will be shared on a secure server, hosted by USC. <https://uscbknpt.sharepoint.com/sites/IPSI/default.aspx> There is a password protected account for PSU members and a separate account for USC members. A list is available documenting team members that have access to the site. Participants are coded with a label and names are not used, however their faces are visible in the videotapes.

9.2 Subject Privacy

Research team can access medical records of stroke patients after completing HIPPA training. Participants can choose to not interact with specific team members if requested, and may decline to provide any personal information. The personal identifiable information will be previously collected from medical record. However, if the participant does not want to answer any questions on the questionnaires, they may choose not to. Researchers will be through in response to participant questions and assure participants that their answers are confidential.

10.0 Data and Safety Monitoring Plan

Not Applicable/minimal risk

10.1 Periodic evaluation of data

10.2 Data that are reviewed

10.3 Method of collection of safety information

10.4 Frequency of data collection

10.5 Individuals reviewing the data

10.6 Frequency of review of cumulative data

10.7 Statistical tests

10.8 Suspension of research

11.0 Risks

Loss of confidentiality is a risk for data analysis and/or chart review research. The techniques employed in this study are non-threatening, non-invasive, and pose no risk beyond that experienced during normal daily activities. In general, subjects may experience fatigue or discomfort due to the two 30 minute increments of sitting.

Because the MRI scanner contains a very strong magnet, participants will not be able to have the MRI if they have certain kinds of metal in your body (for example, a heart pacemaker, a metal plate, certain types of heart valves or brain aneurysm clips). Someone will ask them questions about this before they have the MRI. Having a MRI may mean some added discomfort to the participant. In particular, they may be uncomfortable inside the MRI scanner if they do not like to be in closed spaces (“claustrophobia”). They may also be bothered by the loud banging noise during the study. Temporary hearing loss has been reported from the loud noise. This is why they

will be asked to wear earplugs. During the procedure, they will be able to talk with the MRI staff through a speaker system. They can tell them to stop the scan at any time.

It is possible that the study procedures (brain MRI scan) could detect a possible unknown medical problem that is unrelated to the purpose of this study. If the research procedures uncover findings that may be important for the participant to know about, such as the possibility of a previously unknown medical condition, a member of the study team may contact them to find out if they would like to learn more. These findings may require additional testing or treatment. The cost of any additional tests or related treatment will be their responsibility.

12.0 Potential Benefits to Subjects and Others

12.1 Potential Benefits to Subjects

There is no guaranteed direct benefit to the research subjects. However, they may increase non-paretic arm function. There is minimal risk to the study participants, so the risk/benefit ratio is quite favorable.

12.2 Potential Benefits to Others

This study addresses important questions regarding motor training in stroke patients. If, as hypothesized, these techniques demonstrate potential as therapeutic agents, this research may lead to clinical intervention research, and ultimately to the development of more effective rehabilitation techniques.

13.0 Sharing Results with Subjects

Not applicable

14.0 Subject Stipend (Compensation) and/or Travel Reimbursements

Subjects will be paid \$50 per visit. Additional travel reimbursement will be given if traveling more than 25 miles from study site, up to \$50 per visit.

15.0 Economic Burden to Subjects

15.1 Costs

not applicable

15.2 Compensation for research-related injury

not applicable

16.0 Resources Available

16.1 Facilities and locations

Hershey Medical Center & University of Southern California

16.2 Feasibility of recruiting the required number of subjects

Previous experience indicates that we can recruit a minimum of 20 eligible participants each year, from each site. This, in combination with the current databases at each site, makes the recruitment goal of 30 participants per year (15 per site), over the four-year course of recruitment (120 total), realistic. The HMC database has every stroke patient that is a patient in the hospital, which is over 100 per month. However, we have selective criteria, therefore we aim to recruit less than 5% of them.

16.3 PI Time devoted to conducting the research

PI will reduce teaching load to less than one class per semester in order to devote more time to this study.

16.4 Availability of medical or psychological resources

Both sites have qualified medical personnel available at each location

16.5 Process for informing Study Team

Personnel will be trained prior to the start of the study. Twice a year researchers will fly between sites to provide refresher training. Meetings will be Skyped between the two sites.

17.0 Other Approvals

17.1 Other Approvals from External Entities

USC's IRB has agreed to let COM IRB be the IRB of record for this study (letter uploaded)

17.2 Internal PSU Committee Approvals

Check all that apply:

- Anatomic Pathology – Hershey only – Research involves the collection of tissues or use of pathologic specimens. Upload a copy of HRP-902 - Human Tissue For Research Form on the “Supporting Documents” page in CATS IRB. This form is available in the CATS IRB Library.
- Animal Care and Use – All campuses – Human research involves animals and humans or the use of human tissues in animals
- Biosafety – All campuses – Research involves biohazardous materials (human biological specimens in a PSU research lab, biological toxins, carcinogens, infectious agents, recombinant viruses or DNA or gene therapy).
- Clinical Laboratories – Hershey only – Collection, processing and/or storage of extra tubes of body fluid specimens for research purposes by the Clinical Laboratories; and/or use of body fluids that had been collected for clinical purposes, but are no longer needed for clinical use. Upload a copy of HRP-901 - Human Body Fluids for Research Form on the “Supporting Documents” page in CATS IRB. This form is available in the CATS IRB Library.
- Clinical Research Center (CRC) Advisory Committee – All campuses – Research involves the use of CRC services in any way.
- Conflict of Interest Review – All campuses – Research has one or more of study team members indicated as having a financial interest.
- Radiation Safety – Hershey only – Research involves research-related radiation procedures. All research involving radiation procedures (standard of care and/or research-related) must upload a copy of HRP-903 - Radiation Review Form on the “Supporting Documents” page in CATS IRB. This form is available in the CATS IRB Library.
- IND/IDE Audit – All campuses – Research in which the PSU researcher holds the IND or IDE or intends to hold the IND or IDE.

- Scientific Review – Hershey only – All investigator-written research studies requiring review by the convened IRB must provide documentation of scientific review with the IRB submission. The scientific review requirement may be fulfilled by one of the following: (1) external peer-review process; (2) department/institute scientific review committee; or (3) scientific review by the Clinical Research Center Advisory committee. NOTE: Review by the Penn State Hershey Cancer Institute Scientific Review Committee is required if the study involves cancer prevention studies or cancer patients, records and/or tissues. For more information about this requirement see the IRB website at: <http://www.pennstatehershey.org/web/irb/home/resources/investigator>

18.0 Multi-Site Research

18.1 Communication Plans

In order to facilitate communication and interaction, Drs. [name] and [name] will communicate weekly and via conference call formally once a month that will include all members of the research teams at both sites. As mentioned, Drs. [name] and [name] have an ongoing collaboration and have an established foundation of communication. [name] and [name], as well as one main representative from each research team, will travel to the other laboratory one time per year, to review methods and materials, prevent drift and to insure consistent procedures between laboratories.

18.2 Data Submission and Security Plan

- De-identified data will be collected at both sites (PSU, USC) and managed using REDCap (Research Electronic Data Capture) at Penn State. REDCap is a secure web application designed to support data capture for research studies, providing user-friendly web-based case report forms, real-time data entry validation (e.g. for data types and range checks), audit trails and a de-identified data export mechanism to common statistical packages (SPSS, SAS, Stata, R/S-Plus).
- The database is hosted at the Penn State Hershey Medical Center and College of Medicine data center, which will be used as a central location for data processing and management. REDCap data collection projects rely on a thorough study-specific data dictionary defined in an iterative self-documenting process by all members of the research team. This iterative development and testing process results in a well-planned data collection strategy for individual studies. REDCap is flexible enough to be used for a variety of types of research and provides an intuitive user interface for database design and data entry.
- De-identified research data generated by the project will be shared through ScholarSphere (<https://scholarsphere.psu.edu/>), the repository service that both the University Libraries and Information Technology Services administer at Penn State. Researchers will be able to access the data via ScholarSphere, which ensures persistent access to deposited content. The data will be discoverable via Google and other major search engines, as well as by request to [name] or [name].
- A master list for data will be kept at each site, locked in filing cabinets in a locked room (previously described).
- Videotapes will be shared for standardization and scoring purposes. They will be shared on a secure server, hosted by USC. <https://uscbknt.sharepoint.com/sites/IPSI/default.aspx> There is a password protected account for PSU members and a separate account for USC members. A list is available documenting team members that have access to the site. Participants are coded with a label and names are not used, however their faces are visible in the videotapes.

